### 4.2 – Secondary endpoints

Secondary endpoints are defined in Table 3 below.

Table 3: Secondary endpoints

Endpoint	Description
Other long-term effectiveness endpoints	
2. Freedom from documented AF/AT*, after one or two procedures, with or without AADs, at 12 months
 
3. Freedom from documented AF/AT*, after one procedure, with or without AADs, at 12 months
 
*Freedom from documented AF/AT is defined as no documented episodes of any atrial arrhythmia > 30 seconds with conventional non-invasive monitoring (Holters, TTM and 12-lead ECG recordings) between 3 and 12 months after index procedure
 
Difference of freedom from arrhythmia between the arms will be analyzed as comparison of survival distributions of the two arms in order to take into account the time to arrhythmia recurrence and the censored data (cf. 6.5 – Evaluation criteria for primary and secondary endpoints)

Long-term safety endpoint	
4. Safety composite endpoint at 12 months: death, cerebrovascular events, or serious treatment-related adverse event

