### 5.3.8 – Blanking periods

After the index procedure, a 6-week absolute blanking period will be applied, during which a repeat procedure is not allowed, only cardioversions are allowed if necessary.

After this absolute blanking period and before the end of the standard 3-month blanking period, a repeat procedure is discouraged but not prohibited. The decision to perform a repeat procedure before the end of the 3-month blanking period is left to the operator's discretion. If a repeat procedure is performed during the 3-month blanking period, the recurrence and the repeat procedure are counted as occurring at 3 months.

After a repeat procedure, a 2-week blanking period will be applied, during which AF/AT recurrences will not be counted. Any re-repeat procedures will be performed outside the study according to the operator's preferred approach and will result in the data being censored at the time of the re-repeat procedure. The patient will however stay in the study for safety purposes.

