## **VI – STATISTICAL CONSIDERATIONS**

### **6.1 – Design, statistical methodology and analytical procedures**

Standard summary statistics will be calculated for all study variables (demographics and outcomes) by study group and for all patients. For continuous variables, statistics will include means, standard deviation and 95% confidence intervals for means when assumptions of normal distribution are not violated. Median and quartiles may also be presented. Categorical variables will be summarized using frequency distributions.

The analysis for the primary endpoint will be a modified Intention-To-Treat (mITT) analysis, allowing exclusion of some randomized subjects in a justified way:

- Patients that are deemed ineligible after randomization or that do not have any AF ablation will be excluded
- Patients in the Tailored group for whom AF cannot be induced and who undergo conventional ablation will be included in this analysis
- Patients lost to follow-up (death, disability, relocation, or drop-out) during the 3-month blanking period will be excluded
- Patients who complete at least their 3-month follow-up but who are lost to follow-up (death, disability, relocation, or drop-out) before the 12-month follow-up will be included in the analysis and the data will be censored
- Patients who undergo a 3rd ablation procedure (re-repeat procedure) will be included in the analysis but the data will be censored at the time of the 3rd procedure.

A per-protocol (PP) population will also be evaluated and will serve as supportive analyses to the mITT analysis. In the PP analysis, the population will be analyzed according to the treatment actually received at the start of the study, and will consist of patients that met all the inclusion criteria, none of the exclusion criteria, were successfully treated, had no important protocol deviations and attended all the scheduled follow-up visits.

 <small>ARTIFICIAL INTELLIGENCE SERVING HEART DISEASE</small>	CLIPL-01-002-E	CONFIDENTIAL
	CLINICAL INVESTIGATION PLAN	F 09 XX 01 Rev.A Page 33/47

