4.1.2 The Modified Intent-to-Treat Population (mITT)

The modified Intention-To-Treat (mITT) set will include all randomized subjects except for:

- Subjects who are deemed ineligible after randomization or who do not have any AF ablation, and
- Subjects lost to follow-up during the 3-month blanking period.

Subjects in the Tailored group for whom AF cannot be induced and who undergo conventional ablation will be included in the mITT analysis.

Subjects who complete at least their 3-month follow-up visit but who are lost to follow-up before the 12-month follow-up visit will be included in the mITT analysis.

Subjects who undergo a 3rd ablation procedure will be included in the analyses but the data will be censored at the time of the 3rd procedure for multiple procedure endpoints.

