4.3 SECONDARY ENDPOINTS

The secondary endpoints are as follow:

- 1. Freedom from AF/AT after one or two procedures at 12 months following index procedure.
- 2. Freedom from AF/AT after a single procedure at 12 months following index procedure.
- 3. The safety endpoint is a composite endpoint, the events of which it is comprised include that of death, cerebrovascular event, or serious treatment-related adverse event at the 12-month timepoint since initial index procedure (this endpoint is inclusive of the Blanking Period marked by the 3 months immediately following the initial index procedure undergone by each enrolled subject).

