4.5.1 Other Adverse Events

All adverse events will be summarized through 12 months. The proportions of subjects with events will be reported. No imputation for missing data is planned.

Tabular summaries by treatment group of all adverse events, adverse device effects, serious adverse events, and serious adverse device effects will be presented.

An adverse event (AE) is defined as any untoward medical occurrence, unintended disease or injury or untoward clinical signs (including an abnormal laboratory finding) in subjects,

users or other persons, whether or not related to the investigational medical device. An Adverse Device Effect (ADE) is defined as an adverse event related to the use of an investigational medical device. A serious adverse event (SAE) is an adverse event that:

- a) led to a death
- b) led to a serious deterioration in the health of the subject, that either resulted in: a life-threatening illness or injury, or a permanent impairment of a body structure or a body function, or in-patient or prolonged hospitalization, or -medical or surgical intervention to prevent life threatening illness or injury or permanent impairment to a body structure or a body function.
- c) led to fetal distress, fetal death or a congenital abnormality or birth defect. A serious adverse device effect (SADE) is an adverse device effect that has resulted in any of the consequences characteristic of a serious adverse event.

The investigator will assess each adverse event for its relationship to the study device, and whether it was anticipated in the protocol. The determination of the relationship between the adverse event and the device is made according to the following definitions:

- Definitely related (causal relationship)
- Probably related
- Possibly related
- Not related
- Unknown.

Acute peri-procedural complications (related to the study procedure and occurring within one week of the ablation procedure), will be specifically analyzed as part of the exploratory endpoints.

5 Assessing the Primary Outcome

Freedom from documented AF between 3 and 12 months following the index ablation procedure will be defined as no documented episodes of AF > 30 seconds with conventional non-invasive monitoring.

The following scenarios result in primary endpoint failure:

- 1) A repeat procedure where AF is confirmed during the procedure (Patient is in spontaneous AF at the beginning of the procedure)

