6.2 BLANKING PERIODS

After the index procedure, a 3-month blanking period + tolerance of 1 week (98 days) will be applied for all efficacy endpoints, during which recurrences of AF/AT (excluding repeat procedure) will not be counted.

If a repeat procedure is performed during the 3-month blanking period (and patient is in spontaneous AF), the recurrence and the repeat procedure will be counted as occurring at 3 months.

If a repeat procedure is performed after the end of the 9th month, the procedure will not be considered for multiple procedures endpoints.

After a repeat procedure, a 2-week blanking period (14 days) will be applied, during which AF/AT recurrences will not be counted. Any re-repeat procedures (repeat procedure #2) will result in the data being censored at the time of the re-repeat procedure.

Note: for the purpose of counting months to establish blanking period boundaries in the study, one month will be considered equal to 30.4 days.

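### In the one-or-two-procedure endpoints, a third ablation is censored even when it is the first sign that two ablations failed

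*SAP*

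**What the plan says.** **Rule.** SAP 6.2: "Any re-repeat procedures (repeat procedure #2) will result in the data being censored at the time of the re-repeat procedure". SAP 4.1.2 gives the scope: "the data will be censored at the time of the 3rd procedure for multiple procedure endpoints". Protocol 5.3.8 has the same rule ("will result in the data being censored at the time of the re-repeat procedure"), and so does protocol 6.1. Neither document counts a third ablation as failure in these endpoints.

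**Endpoints affected.** The first secondary endpoint is "Freedom from AF/AT after one or two procedures at 12 months following index procedure". SAP 4.3.1 gives it its own superiority statement at one-sided 0.025, and SAP 6.9 applies no multiplicity correction. The exploratory endpoints that allow more than one procedure are also affected.

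**What counts as an event.** Protocol 4.2 defines freedom from AF/AT as "no documented episodes of any atrial arrhythmia > 30 seconds with conventional non-invasive monitoring" between months 3 and 12. SAP 6.2 adds: "After a repeat procedure, a 2-week blanking period (14 days) will be applied, during which AF/AT recurrences will not be counted".

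**Repeat procedures in the primary endpoint.** The first failure scenario in SAP section 5 is "A repeat procedure where AF is confirmed during the procedure", which the SAP limits to patients in spontaneous AF at the start. SAP 6.2 also counts such a repeat when it falls inside the index blanking period, dating it at 3 months.

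**Sensitivity analyses.** SAP 4.3.2 repeats the two secondary efficacy analyses in the per-protocol population. The missing-data analyses in SAP 6.3 cover only the primary endpoint. Nothing tests the censoring rule.

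**The concern.** Kaplan-Meier, log-rank and Cox analyses assume that a censored patient has the same future risk as patients still under observation. A third ablation within 12 months normally means that the arrhythmia came back after two, so censoring at that date is informative. The SAP's argument for harmless censoring (6.3) is that the burden of participation is equal between arms. That concerns drop-out, not re-treatment for recurrence.

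At stake is an endpoint with its own superiority claim. Only the patient is blinded (protocol 5.1.1), treatment of recurrences is left to the physician (5.3.6), and the redo technique differs by arm (5.3.7). Third ablations could therefore differ between arms, although the documents give no evidence that they will or in which direction.

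**Working it through.** **1. Who is affected.** These are time-to-first-event endpoints.

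- AF/AT documented after the 14-day blanking and before the third ablation: event at that recording. Later censoring does not undo it.
- Recurrence only inside the 14 days: not counted, then censored.
- A home-monitor (TTM) strip never confirmed on another day (SAP section 5, written for AF), with no supporting ECG: not an event, then censored.
- Arrhythmia first confirmed at the third procedure: event and censoring share a date, and no rule says which prevails.

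Only the last three groups matter.

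**2. Number of patients and largest shift.** Inputs: 292 evaluable, 146 per arm (SAP 4.2.2), and 22–33% with a second ablation (SAP 6.9). Assumed, because the documents are silent: a share t of redo patients who have a third ablation, and a share u of those with no earlier event.

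Patients changed = N × redo × t × u. Largest shift in the event-free rate = redo × t × u.

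- t = 5%, redo 22%, u = 1: 292 × 0.22 × 0.05 = 3.2 patients, 1.1 points.
- t = 10%, redo 33%, u = 1: 292 × 0.33 × 0.10 = 9.6 patients, 3.3 points.
- t = 10%, u = 0.5: 0.22 × 0.10 × 0.5 = 1.1 points, to 0.33 × 0.10 × 0.5 = 1.65 points (1.6 to 2.4 patients per arm).
- Wider range: t = 5%, redo 22%, u = 0.1 gives 0.1 points; t = 20%, redo 33%, u = 1 gives 6.6 points.

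**3. Effect on the test.** The plan states no expected AF/AT freedom after two procedures, so its 62% and 77% for single-procedure AF serve as stand-ins. The plan's own figure reproduces: HR = ln 0.77 / ln 0.62 = 0.547, and log-rank power at N = 292 (Lakatos, one-sided 0.025) is 80.0%.

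Simulation: 146 per arm, exponential times, 4,000 runs per row (standard error near 80% power: √(0.8 × 0.2 / 4000) = 0.6 points). A share of failures is censored at the failure time instead of being counted.

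True rates 62% and 77%, same share censored in both arms:

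| Failures censored | Patients (anatomical / tailored) | Anatomical curve | Tailored curve | Power |
|---|---|---|---|---|
| 5% | 2.8 / 1.7 | 61.9 → 63.5% | 77.1 → 78.1% | 82.2 → 80.2% |
| 10% | 5.5 / 3.4 | 62.0 → 65.1% | 77.0 → 79.0% | 81.2 → 76.8% |

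No true difference (62% in both arms), more censoring in the tailored arm:

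| Failures censored (anatomical / tailored) | Patients | One-sided error |
|---|---|---|
| 1.25% / 2.5% | 0.7 / 1.4 | 0.023 → 0.029 |
| 5% / 10% | 2.8 / 5.6 | 0.023 → 0.045 |
| 0% / 5% | 0 / 2.8 | 0.025 → 0.047 |
| 0% / 10% | 0 / 5.6 | 0.028 → 0.078 |

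The unequal rows are illustrations of direction, not forecasts. An excess in the anatomical arm would favour that arm instead.

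**The case against.** **Most double failures are already counted.** A reader might infer that patients who fail two ablations generally leave the risk set as unknowns. The documents do not support that. Patients record weekly and whenever symptomatic (protocol 5.3.5) and have an ECG at unscheduled visits (5.3.6). SAP section 5 lets a 12-lead ECG document AF when there are symptoms, several ECGs at one visit, or a single positive strip in an adjacent week. The time window is also short: the redo falls in months 3–9 and the third ablation must come before month 12. All of this stands. It makes the affected group small, but not empty.

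**No outright contradiction with the primary rule.** SAP 4.3.1 presents the secondary tests as an expansion of the primary endpoint, so the first scenario of section 5 could be read as carrying over. A third procedure begun in spontaneous AF would then be an event. That reading is reasonable, but the SAP does not state it, and section 6.2 taken literally gives censoring.

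**No demonstrated bias towards the tailored arm.** A reader might take the raised error rates as evidence of a false-positive risk. They need more censored failures in the tailored arm, which nothing in the documents predicts. With equal rates the effect works against showing superiority.

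**Censoring was deliberate.** Protocol 5.3.8 and 6.1 and SAP 4.1.2 and 6.2 agree, and the protocol places third procedures outside the study. In addition, counting every third ablation as failure would let an unblinded operator's decision create an event without a core-lab recording, which is broader than the primary rule. This point stands and limits the main-analysis change to procedures begun in spontaneous arrhythmia.

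**Conclusion.** The concern holds for patients who reach a third ablation without an earlier qualifying recording. Their censoring is informative and overstates AF/AT freedom in the first secondary endpoint and the exploratory multiple-procedure endpoints. The documents do not fix the size: it is about 1–3 points at most with an assumed 5–10% of redo patients having a third ablation and no earlier event in any of them, and less otherwise. The effect on the comparison depends on the balance between arms. Equal rates mainly lift both curves and cost a little power, while unequal rates favour the arm with more third ablations. The primary test and the sample size are untouched, since SAP 4.1.2 confines the rule to multiple-procedure endpoints (6.2 repeats it without that limit). A change is justified because the endpoint carries a superiority claim and no planned analysis would show the effect.

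**What to change.** In SAP 4.1.2 and 6.2, for multiple-procedure endpoints only:

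- (a) Count a third procedure begun in spontaneous AF or AT (whichever the endpoint counts) as an event on its date, matching the first scenario in SAP section 5. An earlier documented qualifying recurrence takes precedence, and an event prevails over censoring on the same date. State how a third procedure inside the 14-day blanking is handled.
- (b) Censor at other third procedures, and pre-specify a sensitivity analysis that counts every third ablation done for AF/AT as failure.
- (c) Report third ablations per arm, with and without an earlier event, and list the change in SAP section 7.

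**Cost.** A few SAP sentences and one additional analysis. The AF/AT-free rates may fall slightly. The rule would depart from protocol 5.3.8 and 6.1. SAP section 3 says that the SAP prevails over the protocol, but the departure still needs the section 7 entry.

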6.3 MISSING DATA MANAGEMENT

Subjects who miss a study visit should be contacted immediately by the Investigational site to determine the reason for the missed visit and to reschedule the visit as soon as possible to meet the study visit window. If the subject cannot be located after 3 attempts by phone, email and/or letter, then the subject will be considered lost to follow-up. All attempts to contact the subjects will be documented and retained in the subject study record. Regarding the main judgement criteria, data will be censored if the patient is lost to follow-up. As the burden of study participation does not differ between the tailored and the anatomical arm, we expect all study losses to be non-differential with respect to treatment assignment. Thus, our results will not be biased because of these losses. Additional supportive analyses will be performed on the primary endpoint to assess the effect of missing data. For missing demographic data, the data will not be replaced because it has no weight on the main judgment criterion. A rigorous monitoring is expected; any missing data will be filled in during these visits.

6.4 POOLING DATA ACROSS CENTERS

The analyses will be presented using data pooled across study sites. Summary statistics for the rate of freedom from AF will be calculated by site. A formal assessment of site-to-site heterogeneity will be assessed using a linear mixed-effects binomial regression model with a logit link function for the event of AF recurrence (corresponding to a difference of proportions analysis). The outcome of the model will be the binary status of AF recurrence per subject (0=Subject did not experience AF recurrence, 1=AF recurrence documented on behalf of subject). The model will include an indicator variable for study arm, AF duration as a fixed effect, site as a fixed effect, and a study arm-by-site interaction term. Within the model results, if the study arm-by-site interaction coefficient has a p-value <0.15, it will be regarded as there being heterogeneity detected between sites. Lastly, poolability by geography (US vs. OUS) will be performed based on linear mixed-effects binomial regression as described above. As US subjects will only be patients with AF duration of 3 months to < 12 months, only OUS patients with AF <12 months will be included in the poolability by country assessment.

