## **V – DESIGN OF THE STUDY**

### **5.1 – General**

#### 5.1.1 – Description of the type of clinical investigation

This study concerns a medical device post-CE marking, and has the following characteristics:

- Interventional: Enrolled patients will undergo an AF ablation
- Prospective: Patients are enrolled prior to undergoing an AF ablation
- Multi-center: This study will take place in several sites, at least 5 different sites with a maximum number of inclusions per site as defined in this protocol (cf. 6.8 – Minimum and maximum number of subjects to be included for each site). A maximum of 8 sites may participate in the United States.
- Controlled: Patients in the Anatomical arm (conventional procedure) constitute the control group
- Randomized, two-arm: At enrollment, the patient is randomized 1:1 to one of the arms, Anatomical or Tailored
- Simple-blinded: The patient is not aware of the randomization

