## 6.8 – Minimum and maximum number of subjects to be included for each site

A maximum of 75 inclusions per site (20% of inclusions) will be allowed in order to prevent site-effect. This limit will ensure a minimum of 5 enrolling sites.

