## 6.9 – Poolability of Sites

All investigational sites will follow the requirements of standardized data collection procedures and forms. The primary efficacy and safety endpoints will be presented separately for each site using descriptive statistics. Poolability of the primary efficacy endpoint across investigational sites will be evaluated using a logistic regression model with a fixed effect for site. If there is a significant effect of site, analysis will be repeated using site as a random effect. Sites enrolling fewer than 5 subjects will be combined to form one quasi site. Additional exploratory analyses may be performed to understand any variations in outcome by site. Assessment of poolability by geography (US vs. OUS) will be performed based on logistic regression as described above. As US subjects will only be patients with AF duration of 3 months to < 12 months, only OUS patients with AF <12 months will be included in the poolability by country assessment. As only one catheter type is approved for use in the US, an additional subgroup analysis of each catheter used will assess the variability, if any, by country for patients with the same catheter type.

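### The site-heterogeneity rule in SAP 6.4 reads one interaction coefficient where its model has at least four, and it uses a yes/no outcome that does not match the time-to-event primary analysis

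*SAP*

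**What the plan says.** SAP 6.4 presents the analyses pooled over sites and adds a formal check of heterogeneity. The model is a logistic one, labelled mixed-effects, and is specified as follows: "The model will include an indicator variable for study arm, AF duration as a fixed effect, site as a fixed effect, and a study arm-by-site". The last of these items is an interaction. The decision rule is that "if the study arm-by-site interaction coefficient has a p-value <0.15, it will be regarded as there being heterogeneity detected between sites". On the outcome it says: "The outcome of the model will be the binary status of AF recurrence per subject", coded "0=Subject did not experience AF recurrence, 1=AF recurrence documented on behalf of subject". The same type of model is then used for US versus non-US, restricted to patients with AF of less than 12 months.

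SAP 6.4 names no joint test, no reference site and no analysis set. It has no rule for patients censored without recurrence and states no action if heterogeneity is found.

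Protocol 6.9 also plans a logistic model, with two provisions that SAP 6.4 does not repeat: "Sites enrolling fewer than 5 subjects will be combined to form one quasi site", and "If there is a significant effect of site, analysis will be repeated using site as a random effect".

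On the number of sites, Protocol 6.8 says of its cap on inclusions: "This limit will ensure a minimum of 5 enrolling sites". Protocol 5.1.1 adds: "A maximum of 8 sites may participate in the United States". Neither document gives a total.

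**The concern.** The rule and the model do not fit together. A single arm-by-site coefficient exists only with two sites. With k sites there are k − 1, each comparing the treatment effect at one site with that at a reference site. The analyst must choose between reading any of them, reading one, or testing them together, and could make that choice after seeing the data. The options have very different false-positive rates, and the outcome is a stated label on the trial: heterogeneity detected or not.

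The second problem is the outcome. The primary analysis is a right-censored time-to-event comparison (SAP 4.2.3 and 6.3), and patients lost after their 3-month visit stay in the mITT set (SAP 4.1.2). Under a 0/1 status, a patient lost at month 5 without documented AF fits only the 0 category, alongside patients followed for the full 12 months. The check therefore concerns a different quantity from the result whose consistency it is meant to support.

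**Working it through.** **Inputs.** Threshold 0.15 and model terms: SAP 6.4. Minimum of 5 sites: Protocol 6.8 (374/75 = 4.99). AF-free rates of 62% and 77%, 292 evaluable and 374 enrolled patients, 22% drop-out: SAP 4.2.2. Site counts above 5 are assumptions.

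**The plan's own figures.** The SAP gives no false-flag rate, so only the design behind the model can be reproduced. HR = ln(0.77)/ln(0.62) = 0.547. The Schoenfeld formula at one-sided 0.025 and 80% power gives 87 events. The average event probability is (0.38 + 0.23)/2 = 0.305, and 87/0.305 = 285.2, or 286 patients, within 3% of 292. With drop-out, 292/0.78 = 374.4, against 374 in the plan.

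**Number of coefficients.** k − 1, so 5 − 1 = 4 at the documented minimum.

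**False-flag rate if any coefficient with p<0.15 counts, with no true interaction.**

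1. Treating the coefficients as independent: 1 − 0.85^(k−1). For k = 5, 1 − 0.85^4 = 0.478. This overstates the rate.
2. Allowing for the shared reference site. With equal sites, each coefficient is a difference between two site-specific effects, and any two coefficients share one of these, so their correlation is 0.5. The probability that at least one exceeds the two-sided 0.15 limit was taken from 400,000 draws.
3. Simulating the SAP's logistic model: 800 trials per setting, five settings per k. N was 292 or 374. Drop-out was 0, 10% or 22% with dropped patients coded 0. One setting had unequal sites, and one had drop-out of 0 or 44% depending on site. The simulation standard error at 40% is √(0.4 × 0.6/800) = 1.7 points.

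| Sites | Coefficients | Independent | Correlated, large-sample | Simulated, any coefficient | Simulated, joint likelihood-ratio test |
|---|---|---|---|---|---|
| 5 | 4 | 47.8% | 40.4% | 40.5–43.4% | 16.8–20.4% |
| 8 | 7 | 67.9% | 54.9% | 49.5–56.2% | 16.6–19.8% |
| 13 | 12 | 85.8% | 69.2% | 50.0–64.1% | 22.8–27.4% |
| 20 | 19 | 95.4% | 80.8% | 40.4–59.6% | 34.0–41.9% |

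Reading one coefficient fixed in advance gave 13–17% at 5 and 8 sites. The joint test is nominally 15%. It drifts upward as cells become sparse: at 20 sites the average site has 292/20 = 14.6 or 374/20 = 18.7 patients over both arms.

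**Does the coding of censored patients add false flags?** At 5 sites the any-coefficient rate was 41.5% with no drop-out (N = 292) and 41.6% with 22% (N = 374). At 8 sites it was 53.9% and 54.6%. With drop-out of 0 or 44% by site, equal between arms, it was 40.5% and 56.2%. None of these differences is distinguishable from simulation error.

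**US versus non-US.** Two regions give 2 − 1 = 1 interaction coefficient, so the 0.15 threshold means what it says there. The outcome mismatch still applies.

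**The case against.** The best defence is that the SAP puts one arm-by-site term in the model and then mentions one p-value, so coefficient is loose wording for a single test of the term, with a nominal rate of 15%. That reading is reasonable, but the SAP does not state it, and a programmer following the text would not be bound to it. It is also fair to say that the check is supportive, that no action is attached to the flag, that the primary log-rank test is untouched, and that the protocol itself planned a logistic model. These points limit the importance; they do not remove the ambiguity.

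Four stronger inferences are tempting and are not supported:

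- That flags would arise mostly by chance, or almost surely. At 5 sites, the only documented count, every calculation is below 50%. Higher rates need assumed site counts, and the highest need independence, which does not hold. A false-flag rate is also not the share of flags that are due to chance.
- That coding censored patients as recurrence-free inflates the flag rate. The simulations show no such effect when loss is equal between arms.
- That the planned 22% drop-out measures how many patients are miscoded. It includes patients with no ablation, who are outside the mITT set, as are those lost in the first 3 months. The documents do not give the share censored later.
- That the SAP repeals the protocol's rule on small sites. SAP section 3 gives the SAP precedence where the two disagree. Not repeating a compatible rule is not clearly a disagreement.

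**Conclusion.** The point holds as a defect in a supportive check. The decision rule refers to one coefficient where the stated model has at least four. If any of them counts, the false-flag rate is about 40% at 5 sites (40.4/15 = 2.7 times nominal) and about 55% at an assumed 8 (54.9/15 = 3.7 times). Under an unstated joint-test reading it is nominally 15%, and 17–20% in the simulations at 5 and 8 sites. The 0/1 outcome is a separate mismatch with the censored primary analysis. That censored patients fall under 0 follows from the two categories offered, not from an explicit SAP rule.

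The figures assume no true interaction, 1:1 allocation and the planned AF-free rates. The simulations further assume exponential recurrence times and drop-out times spread evenly over follow-up. The conclusion on the primary endpoint does not depend on any of this.

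**What to change.** Replace the rule in SAP 6.4 with the following: fit the primary Cox model in the mITT set with arm, AF duration, site and arm-by-site, and test all arm-by-site terms with one likelihood-ratio test on (k − 1) degrees of freedom at 0.15. Carry over from Protocol 6.9 the combining of sites with fewer than 5 subjects, and count k after combining. For US versus non-US, use the same Cox model with its single arm-by-region term. Say what follows a positive result, including whether the protocol's repeat analysis with site as a random effect still applies.

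The joint test can still exceed 15% with many small sites, which is why small sites must be combined. Combining at 5 may not be enough: the simulated 20-site settings averaged well above 5 patients per site and still gave 34–42%, in the logistic model (the Cox version was not simulated). If the final site count is of that order, the SAP should set a higher limit for combining or calibrate the joint p-value by simulation under the no-interaction model.

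The cost is a few lines of SAP text and code. No new data are needed.
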